9.10 Follow-up assessments

The patients mentioned below will be in follow-up, if possible until death up to the end of the study:

- the patients who complete the first 3 years of maintenance and whose MRD was not informative at baseline
- the patients who discontinue the study treatment
- the first patients who complete the 6 years of maintenance

Thereafter, the long term follow-up of patients will be organized for further analysis.

The following assessments must be conducted every 3 months during the first 2 years, then every 6 months until the last visit of the last patient.

9.10.1 Patients who have discontinued treatment due to reasons other than progressive disease or relapse (meaning patients who did not experienced progression or relapse)

The following parameters will be assessed:

- Physical examination
- ECOG PS
- Blood cell counts: Hemoglobin, leukocyte count, neutrophils, lymphocytes, platelets and lymphoma cells
- Thorax, abdomen and pelvis CT with IV contrast every year
- Any other evaluations or procedures for evaluation of the treatment response.
- Evaluation of the treatment response (Cheson 1999: **see Appendix 8** "Response criteria for lymphoma")

Patients included in the study who withdraw before study treatment start will not be followed.

9.10.2 Patients who experienced progressive disease or relapse

Only survival status and other malignancies will be recorded at every evaluation period.

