Safety consideration	
Time of Analysis
 
Given the fact that primary endpoint is prematurely determined in study treatment period, 2 types of analysis will be performed:
 
 • Primary criterion analysis • Final analysis 
Primary criterion analysis:
 
Primary criterion analysis will be performed once all patients included in efficacy set (70 evaluable patients) have completed 4 cycles of treatment or treatment discontinued prior to cycle 4 of the study and will consist of analyzing:
 
 • Primary criterion : MRD rate in bone marrow after the 4 cycles or at treatment discontinuation of GA-DHAP • Treatment exposure • Stem cell collection failure • Secondary safety endpoints 
Final analysis:
 
All analyses will be performed when all included patients will have performed the end of treatment visit (end of maintenance “on demand” period or treatment discontinued from the study).
 
 • AE of grade 3-5 (CTCAE – v 4.03) regardless the relationship to IMP occurring from the date of informed consent signature, and up to 28 days after last treatment administration, will be recorded on the AE pages of eCRF. • Some adverse events which are attributable to the ASCT procedure only and not to the study drug are not to be entered in the eCRF (listed in section 14.2). • Any grade for AESI will be collected from ICF signature and until 28 days after last treatment administration regardless the relationship to IMP • All events that meet one or more criteria of seriousness, regardless the relationship to IMP, occurring from the date of the informed consent signature, during treatment administration period and up to 28 days after last drug administration, will be reported as SAE.

	
A SAE that occurs after this time, including follow up period, will be reported if considered related to IMP.
 
In a case of SAE the Investigator must immediately (within 24 hours):
 
SEND the SAE pages to LYSARC Pharmacovigilance department: [contact] OR EMAIL TO [contact]
 
Pregnancy and suspected pregnancy will be reported on Pregnancy Form to LYSARC PV from the date of informed consent signature and up to 28 days after the last study drug administration.

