9.8 Evaluation during maintenance

	When
Clinical examination	Before each GA101 injection*
ECOG PS	Before each GA101 injection*
Blood cell counts: Hemoglobin, leukocyte count, neutrophils, lymphocytes, platelets and lymphoma cells	Before each GA101 injection*
Thorax, abdomen and pelvis CT with IV contrast (Disease response assessment results must be available and reviewed by the investigator before the first dose of study drug in the next planned cycle)	Every 6 months during 3 years then once a year
FDG-PET (Evaluation of the disease response : the Lugano classification 2014)	At the end of the first 3 years of maintenance
Evaluation of the disease response (Cheson 1999)	Every 6 months during 3 years then once a year
Any other evaluations or procedures performed at baseline for evaluation of the disease response	Every 6 months during 3 years then once a year
Samples for MRD study : - BM aspiration - Blood sampling	- At the end of the first 3 years of maintenance - Every 6 months during the 1st 3 years then every 3 months during the 3 following years
The adverse events reporting	Continuous

***MRD negative patients** after 3 years of maintenance will be evaluated every 3 months during the 3 following years. Samples for MRD study will be performed as indicated above.

The following parameters will be assessed:

- Physical examination
- Blood cell counts as described above
- Thorax, abdomen and pelvis CT with IV contrast every year
- Any other evaluations or procedures for evaluation of the treatment response.
- Evaluation of the treatment response (Cheson 1999)

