14.3 Serious Adverse Events reporting rules

All events that meet one or more criteria of seriousness (see Section 13.1.2.) will be reported **continuously** from the date of informed consent signature to 28 days after the last study drug administration of the maintenance period. During maintenance on-demand, if GA101 is discontinued (temporarily or permanently), SAEs will be reported until 28 days after last study drug administration. If GA101 is reintroduced (according to MRD results), SAEs will further be reported according to the same reporting rules.

SAE will be reported regardless:

- the relationship to the study treatment
- the administration of new lymphoma therapy,
- disease progression.

Nevertheless, the following SAEs that occur during maintenance on-demand beyond 28 days after the last administration of GA101 will be reported as SAEs regardless relationship to study treatment:

- Death
- Life-threatening events
- Severe infections, hepatitis, progressive multi-focal encephalopathy
- Cardiac events
- Neutropenia

To note that all SAEs **considered related to the study medication** will **always** be reported even if occur beyond 28 days after the last administration of GA101 including during the follow-up period.

Whenever possible, symptoms should be grouped as a single syndrome or diagnosis. The investigator should specify the date of onset, intensity, action taken regarding the study medication, corrective therapy given, outcome of all SAEs and his/her opinion as to whether the SAE can be related to the IMP.

General SAE reporting rules:

- Any episode of any grade of toxicities, which meets one of the seriousness criteria must be reported as "Serious Adverse Event" in the appropriate SAE form
- Signs, symptoms and physical findings indicative of lymphoma or progression of lymphoma are not to be reported as "Serious Adverse Event"
- Hospitalizations **not to be considered** as SAE are:
 - Planned hospital admissions or surgical procedures for an illness or disease which existed before the patient was enrolled in the study or before the study drug was given are not to be considered SAEs unless the condition deteriorated in an unexpected manner during the study (eg surgery was performed earlier than planned).
 - A procedure for protocol therapy administration or protocol/disease-related investigations. Hospitalization or prolonged hospitalization for a complication will be reported as an SAE

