### 5.10.3 Other Primary Malignancy (OPM)

**Table 5.10.4 OPM – Safety set**

		Safety set N=XX
Patients with at least one OPM		
No		XX (XX.X%)
Yes		XX (XX.X%)
If yes, number of OPMs by patient		
N		XX
Missing		XX
Mean (SD)		XX.X (XX.XX)
Median		XX.X
Q1 ; Q3		XX ; XX
Min ; Max		XX ; XX
If yes, time to onset of 1st OPM since inclusion (months)		
N		XX
Missing		XX
Mean (SD)		XX.X (XX.XX)
Median		XX.X
Q1 ; Q3		XX ; XX
Min ; Max		XX ; XX

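### Off treatment, other malignancies are solicited only after progression, so the SAP's Safety Set table of other primary malignancies is likely to under-count cases in remission

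*Protocol*

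**What the plan says.** **Protocol, after progression.** Section 9.10.2 states: "Only survival status and other malignancies will be recorded at every evaluation period".

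**Protocol, off treatment without progression.** Section 9.10.1 covers "Patients who have discontinued treatment due to reasons other than progressive disease or relapse". Its list has examination, ECOG status, blood counts, yearly CT, response, and "Any other evaluations or procedures for evaluation of the treatment response". It does not mention malignancies or adverse events.

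**Protocol, off drug in the on-demand phase.** Under the starred note in 9.8, MRD-negative patients "after 3 years of maintenance will be evaluated every 3 months during the 3 following years". The parameters listed are examination, counts, yearly CT and response evaluations.

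**Protocol, safety windows.** Section 14.2 collects grade 3-5 AEs until 28 days after the last study drug. Section 14.3 sets the same limit for SAEs, with two exceptions. The first begins: "Nevertheless, the following SAEs that occur during maintenance on-demand beyond 28 days after the last administration of GA101 will be reported as SAEs", whatever the causality; the list is death, life-threatening events, severe infections with hepatitis and PML, cardiac events and neutropenia. The second keeps SAEs related to study medication reportable without time limit. The synopsis words this as: "A SAE that occurs after this time, including follow up period, will be reported if considered related to IMP".

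**SAP.** Section 5.10.3 has a yes/no row, "Patients with at least one OPM", with the number per patient, time from inclusion to the first one, a SOC/PT table, a listing and narratives. All are on the Safety Set, which is every consented patient with at least one dose.

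**The concern.** The protocol asks for this item by name in one group of off-treatment patients and not in the others. The SAP then pools all of them. A patient in remission whose malignancy was never asked about is counted as a No and stays in the denominator.

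The incidence would therefore mix two levels of ascertainment: solicited at each evaluation after progression, and largely dependent on causality, seriousness or chance in remission. Time to onset is affected too. It is summarised among recorded cases only, without censoring, so it leans towards events on treatment and after progression. What is at stake is a late-risk description for a regimen that can run about six years beyond transplant. No decision rule and no primary-endpoint figure depends on it.

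**Working it through.** The documents give no figure for other malignancies, so there is none to reproduce. The check sets the collection rules side by side and then works out how long the gap lasts.

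**Step 1: routes for a malignancy arising more than 28 days after the last dose.**

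- *Progressed or relapsed:* asked for at each evaluation (9.10.2).
- *Not progressed, treatment stopped:* not listed (9.10.1).
- *MRD-negative and off drug in the on-demand phase:* not listed (9.8, starred note).
- *Completed six years, or completed three years with non-informative baseline MRD:* followed under 9.10. The heading of 9.10.1 speaks of discontinuation, although its bracketed gloss can be read to include them. Either way the item is absent.
- *Appendix 3, follow-up column:* no malignancy item.
- *AE rules:* closed (14.2).
- *Late SAE list, any causality:* malignancy not named, and the list is confined to the on-demand phase (14.3).
- *AESI:* tumour lysis syndrome and grade 4 infusion reactions only (14.5).
- *Related SAE:* open without time limit (14.3, synopsis).

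What remains uncovered in remission is a malignancy judged unrelated that is neither fatal nor life-threatening.

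**Step 2: length of the gap for a patient who stays MRD-negative and never restarts.**

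Inputs are three 21-day intervals to D1 of cycle 4 (63 days), conditioning 4 to 8 weeks later, 8 days to graft, maintenance 2 to 3 months after transplant, 36 months of maintenance, then 36 months on-demand. One month is 30.4375 days.

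- Start of maintenance: (63 + 28 + 8)/30.4375 + 2 = 5.3 months after C1D1 at the short end; (63 + 56 + 8)/30.4375 + 3 = 7.2 months at the long end.
- General window closes: start + 36 + 28/30.4375 = 42.2 to 44.1 months.
- Planned course ends: start + 72 = 77.3 to 79.2 months.
- Gap: 36 - 0.92 = 35.1 months, or 2.92 years. That is 35.1/77.3 = 45% to 35.1/79.2 = 44% of the planned course.
- For an early patient followed about 100 months (November 2016 to Q1 2025): (100 - 42.2)/100 = 58% to (100 - 44.1)/100 = 56%.

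**Step 3: illustration on assumed inputs.**

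None of the following comes from the documents, except that 70 and 83 are the planned evaluable and enrolled numbers. Assume 70 to 83 treated, 40% to 70% of them in remission and off drug for the whole phase, and 0.5% to 2% malignancies per year.

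Expected cases arising in the gap = treated × fraction × rate × 2.92.

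- Low: 70 × 0.40 × 0.005 × 2.92 = 0.4.
- High: 83 × 0.70 × 0.02 × 2.92 = 3.4.
- If half were judged related and reported, the unreported number is 0.2 to 1.7.

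With 83 treated, one missed case is 1/83 = 1.2 percentage points of incidence.

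**The case against.** The strongest reply is that the follow-up lists are not exhaustive. Section 9.10.1 also omits survival status, yet OS is analysed on the Safety Set, and 9.2 describes its schedule as a minimum. On that view, the restriction in 9.10.2 trims a fuller follow-up and does not add an item unique to progressed patients. The eCRF is not among the documents, and the SAP's full set of OPM outputs is consistent with a form open to everyone.

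This has weight, and such a form cannot be excluded. But survival is required elsewhere for all patients, through 9.10 and the OS definition. Other malignancies off treatment are required nowhere else in the supplied text, so the asymmetry in the plan stands.

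A second reply is that other routes exist, and this limits the claim. A reader might infer that a malignancy in remission has no way into the data, or only if attributed to obinutuzumab. The documents do not support either reading:

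- Related SAEs are always reportable. Section 14.3 speaks of study medication where the synopsis speaks of the IMP, and the SAP tabulates relationship to DHAP and ASCT. Whether an event attributed to BEAM qualifies is therefore unclear, not settled against reporting.
- Deaths, life-threatening events and neutropenia SAEs are reportable in the on-demand phase whatever the cause.
- Concurrent illness or another anti-neoplastic therapy can end treatment, and 13.1 requires the reason to be reported.
- SAP 5.12 tabulates anti-cancer therapy given outside progression.
- Examinations and yearly CT may find cases incidentally.

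Nor is capture after relapse shown to be complete; it is solicited, which is a weaker statement.

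A third reply is that other malignancy is not a separately named protocol endpoint and is only described in a single-arm phase II trial. That is fair, and it bounds the importance.

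**Conclusion.** The point holds as a matter of unequal ascertainment. Followed as written, the plan asks about other malignancies off treatment only after progression, and the SAP reports them on everyone without a collection window, a split by progression status or a caveat. The likely direction for incidence is under-counting in remission. For time to onset, the documents do not fix the direction of the distortion.

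The size cannot be derived. Roughly 0 to 3 cases is an illustration resting on the assumed rate, the assumed fraction in remission and off drug, and the share captured by other routes.

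Two further inferences should be avoided:

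- The 20-25% MRD positivity in Protocol 11.3.1 cannot be turned into a number of untreated patients or a firm count of missed cases. It is a percentage of samples from another cohort in the first three years, and the same section gives less than 20% later. Patients may also convert and restart treatment.
- Section 5.1 does not flag myelodysplasia as a hazard of this regimen. It cites a lower risk with BEAM than with total body irradiation, as one reason for using BEAM.

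The conclusion assumes that no eCRF page outside the supplied documents already solicits the item from all patients. If one does, the remedy reduces to saying so in the protocol and SAP.

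**What to change.** **Protocol.** Add other malignancies, any causality and with date of diagnosis, to the 9.10.1 list, the off-drug list in 9.8, the Appendix 3 follow-up column and the late-SAE list in 14.3. Apply this to all Safety Set patients through end of study, and state that it includes patients who complete treatment.

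**Where visits are already complete.** SAP version 2.0 is dated October 2024 and the last visit is planned for Q1 2025, so a prospective question may recover little. In that case, either send sites a one-time query before database lock asking for any other malignancy since inclusion in every treated patient, or present the 5.10.3 tables by collection window and progression status with a note on unequal capture.

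**Cost.** One question at visits that already exist, a short amendment or eCRF query, and a few more forms. The SAP-only option costs a table split and a footnote, but describes the under-count without repairing it. No sample-size or error-rate figure changes.

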9.11 Progression/relapse

Relapse/progression will be determined as per Cheson 1999 criteria (see Appendix 8 “Response criteria for lymphoma”)

Progressive disease should be based on CT scan and not PET or MRD.

A pathological confirmation by biopsy of the lesion should be done if possible.

10 TREATMENTS

10.1 Drugs description, storage, handling and administration

Drugs composing the DHAP and conditioning regimen for transplant are registered and are available at the hospital pharmacy.

Chemotherapy products are to be used according to summary of product characteristics.

Obinutuzumab is considered as investigational medicinal product (IMP) and will be supplied by Roche from induction to maintenance.

10.1.1 *Obinutuzumab: Description*

Obinutuzumab as know as GA101 is a humanized glycoengineered type II anti-CD20 monoclonal antibody that recognizes the CD20 antigen present on normal and malignant B cells and is being developed for the treatment of hematological malignancies including NHL and CLL.

10.1.2 *Obinutuzumab: Packaging*

Obinutuzumab is provided as a single-dose, sterile liquid formulation in a 50mL pharmaceutical grade glass vial containing a nominal 1000 mg of Obinutuzumab (G3 material). The formulated drug product consists of 25 mg/mL drug substance (G3) formulated in histidine, trehalose, and poloxamer 188. The vial-contains 41 mL (with 2.5% overfill).

10.1.3 *Obinutuzumab: Storage conditions*

The recommended storage conditions for the Obinutuzumab drug product are between 2°C to 8°C protected from light. Chemical and physical in-use stability for Obinutuzumab dilutions in 0.9% sodium chloride in the concentration range from 0.2 to 20mg/mL have been demonstrated for 24 hours at 2°C to 8°C and at ambient temperature and ambient room lighting. The prepared diluted product should be used immediately. If not used immediately, in-use storage times and conditions prior to use are the responsibility of the user and would normally not be longer than 24 hours at 2°C to 8°C. Obinutuzumab should not be frozen or shaken. Mix gently. All transfer procedures require strict adherence to aseptic techniques. Do not use an additional in-line filter due to potential adsorption.

10.1.4 *Obinutuzumab: Handlings*

Obinutuzumab should be given as a slow IV infusion. It should not be administered as an IV push or bolus. Obinutuzumab infusions should be made through a dedicated line. Isotonic 0.9% sodium chloride solution should be used as the infusion vehicle. Obinutuzumab will be administered at the flat dose of 1000mg.

Reconstituted Obinutuzumab drug product intended for IV infusion is prepared by dilution of the drug product into an infusion bag containing 0.9% sodium chloride, to the final drug concentration of 4 mg/mL.

Dilution preparation:

Using a 250-mL infusion bag containing 0.9% sodium chloride, withdraw and discard 40 ml of the sodium chloride.

Withdraw 40 ml of Obinutuzumab from a single glass vial and inject into the infusion bag (discard any unused portion of Obinutuzumab left in the vial). Gently invert the infusion bag to mix the solution; do not shake.

10.1.5 **Obinutuzumab: Administration**

See also section 10.5.1. *Infusion-Related Reactions related to Obinutuzumab* and section 10.5.2 *Tumor Lysis Syndrom*

Infusion rates of Obinutuzumab will be managed as follows:

Administration of First and Subsequent Infusions of GA101

First Infusion (Day 1 of Cycle 1)	Subsequent Infusions

 • Begin infusion at an initial rate of 50 mg/hour. • If no infusion-related or hypersensitivity reaction occurs, increase the infusion rate in 50-mg/hour increments every 30 minutes, to a maximum of 400 mg/hour. • If a reaction develops, stop or slow the infusion. Administer medications and supportive care in accordance with institutional guidelines. If reaction has resolved, resume the infusion at a 50% reduction in rate (i.e., 50% of rate being used at the time that the reaction occurred). 	
 • If the patient experienced an infusion-related or hypersensitivity reaction during the prior infusion, use full premedication including 100 mg prednisone/prednisolone (until no further IRR occurs), begin infusion at an initial rate of 50 mg/hour and follow instructions for first infusion. • If the patient tolerated the prior infusion well (defined by an absence of Grade 2 reactions during a final infusion rate of ≥ 100 mg/hour), begin infusion at a rate of 100 mg/hour. • If no reaction occurs, increase the infusion rate in 100-mg/hour increments every 30 minutes, to a maximum of 400 mg/hour. • If a reaction develops, stop or slow the infusion. Administer medications and supportive care in accordance with institutional guidelines. If reaction has resolved, resume the infusion at a 50% reduction in rate (i.e., 50% of rate being used at the time that the reaction occurred).

In all parts of the study, Obinutuzumab must be administered in a clinical (inpatient or outpatient) setting. Full emergency resuscitation facilities should be immediately available and patients should be under close supervision of the investigator at all times.

Obinutuzumab should be administered as a slow IV infusion through a dedicated line. For patients who are considered to be at risk of tumor lysis syndrome (TLS) with a high lymphocyte count or bulky lymphadenopathy, the infusion have to be given extremely slowly (25 mg/hour) over a long period of time or the dose may be split and given over more than one day. The first recommended dosage is 100 mg followed by 900mg administered on day 1 or day 2. All patients considered at risk should be carefully monitored during the initial days of treatment with a special focus on renal function, potassium, and uric acid values.

IV infusion pumps should be used to control the infusion rate of Obinutuzumab. Do not administer as an IV push or bolus. Administration sets with PVC, PUR, or PE as a product contact surface and IV bags with PO, PP, PVC, or

PE as a product contact surface are compatible and can be used. Do not use an additional in-line filter because of potential adsorption.

After the end of the first infusion, the IV line or central venous catheter should remain in place for ≥ 2 hours to be able to administer IV drugs if necessary. If no adverse events occur after 2 hours, the IV line may be removed or the central venous catheter may be de-accessed. For subsequent infusions, the IV line or central venous catheter should remain in place for at least 1 hour after the end of the infusion. If no adverse events occur after 1 hour, the IV line may be removed or the central venous catheter may be de-accessed.

For further information on description, storage, handling and administration please consult the Investigators Brochure (IB).

